2.2.5. Spatial Navigation Experiments

We have preliminary data showing that sensory flicker may decrease the rate of interictal epileptiform discharges (IEDs), which constitute abnormal brain activity often detected in epilepsy patients. In the following experiments, we will further test the effects of sensory flicker on the rate of interictal epileptiform discharges, while the patient performs a spatial navigation task described below. The simultaneous running of the spatial navigation task will be used to control for subject's attention and arousal state, which has been shown to influence the rate of IEDs.

Spatial navigation task:

In this task, subjects learn the layout of a computer-generated virtual city environment and the locations of landmarks by navigating from a first-person perspective using a game controller or keyboard⁴³. Each session (virtual day) of the task consists of 12 virtual city environments where subjects navigate for 9 minutes. There are hidden shortcuts to goal landmarks where subjects learn to find as they are instructed to navigate to goal landmark as quickly as possible. Behavioral records from the memory testing (e.g. keystrokes, in the form of game controller or keyboard inputs) will be collected.

During these experiments, the patient will do the spatial navigation task above while being exposed to sensory flicker via glasses lined with LEDs with see-through holes, and earbuds or headphones. Subjects may be exposed, up to 60 minutes at a time, to visual and/or auditory flicker at frequencies anywhere between 3-200Hz.

2.2.6. Electrical brain stimulation

To contrast the effects of sensory versus direct electrical flicker stimulation on neurophysiology and cognition (such as memory), we will stimulate various brain regions at various frequencies ranging from 5-200Hz, for up to 10 seconds at a time. We will initially be testing specifically frequencies of 5.5Hz and 40Hz.

During brain stimulation sessions, bipolar electrical stimulation will be applied to one or more areas of the brain at a time either with or without associated memory task. Stimulation in the

absence of any memory task will be applied in order to assess the subject's neurophysiological response to stimulation and to identify the optimal stimulation parameters for use during memory task. Stimulation during memory task will be applied in an attempt to affect the subject's memory.

The proposed intracranial stimulation parameters are both historically common and proven safe in epileptic populations. Stimulation will be current-regulated and charge-balanced, with biphasic rectangular pulses. The anticipated electrode impedance is 1-4 kΩ. Stimulation will be bipolar, involving adjacent electrodes. Prior to testing, current amplitude will be increased in a stepwise fashion in order to identify the threshold for afterdischarge (anticipated range from 0.2mA to less than 8mA), and then decreased by 25-30% for the duration of testing. If no after-discharges are observed, the maximum amplitude of current will be kept under 8mA.

These parameters are considered safe and well tolerated in patients with epilepsy who have depth electrodes implanted in the amygdala and hippocampus for both clinical and research endeavors^{10,25,34,26-33}. Furthermore, these parameters are similar to intracranial stimulation parameters used in other ongoing translational research protocols at Emory University Hospital^{35,36}.

2.2.7. Memory encoding experiment

To determine whether audiovisual flicker impacts recognition memory, subjects may be asked to perform a memory task in which they view a series of images or words from a standard set. Memory for these items will be assessed at the end of the initial session or 1 day later. The general paradigm is based on memory enhancement experiments from our team using amygdala electrical stimulation¹², that have previously been approved by the Emory IRB (IRB00067252).

The subject will be presented with a series of images or words referring to objects. Each item will be presented only briefly (e.g., 3 sec). During presentation of items in the study phase, the subject will be asked to state an intrinsic characteristic of the object (e.g., whether the object is used indoors or outdoors). Presentation of some of these items will be paired with brief (e.g. 1-10 seconds) audiovisual flicker. During presentation of items in the test phases, the subject will be asked to determine whether he or she has previously seen the exact object (e.g., Yes / No) and to gauge his or her confidence in this response (e.g., Low / High).

Trials will be divided into blocks, with extended delay periods (e.g., 10-20 sec) allowing the subject to rest briefly at several points throughout the study phase; the test phases will be self-paced. The anticipated duration of the experiment is about 55-75 min on day 1 and 15-20 min on day 2.

2.2.8. Memory consolidation experiment

To determine whether audiovisual flicker impacts memory consolidation, subjects may go through the following experimental paradigm or a similar one, based on Roberts et al.'s (2018)¹³ experiment (Figure 5).

Patients will view 4 series of words or images. In 2 of these series, they will be asked for each word or image whether it refers to a living thing, while in the other 2 series, they will be asked whether each word or image refers to something that is man-made. This will be followed by a 36-minutes period of exposure to audiovisual flicker (either random or 5.5Hz or 40Hz, via the customized DAVID device). Finally, they will undergo an unexpected test of memory for the words or images they've been exposed to (item recognition), as well as the associated contextual sorting they had to perform (alive vs man-made, i.e. source recognition).

For this experiment, depending on his or her choice, a patient may go through the task more than once on different days, being exposed to a different condition each time (random, 5.5Hz, or 40Hz audiovisual flicker). This would allow us to compare the effects of specific frequencies of audiovisual flicker on memory, in the same patients.

[figure not shown]

Figure 5: experimental paradigm from Roberts et al. (2018). In our experiment, we may use images instead of words, and patients will be tested for effects of either random, 5.5Hz or 40Hz audiovisual flicker on memory. In case a patient were to be tested for the effects of more than one type of sensory flicker, he or she would be tested for each type of sensory flicker on different days.

The anticipated duration of this experiment is about 120min for each day.

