1.3.1. Primary Outcome Measures

The primary outcome measure is the effect of sensory **flicker** exposure on local field potential (LFP): comparing mean power spectral density at the frequency of flicker being presented between flicker and baseline periods. [Time Frame: Up to 6 weeks]

Power spectral density of the LFP will be measured across stimulus frequencies and modalities of sensory flicker stimuli in visual areas, auditory areas, hippocampus and prefrontal cortex. The mean power spectral density measured in dB at the frequency of flicker being presented will be compared between flicker stimulation and no-stimulation baseline periods.

1.3.2 Secondary Outcome Measures:

The secondary outcome measure is the effect of sensory flicker on interictal epileptiform discharges (IEDs), which represent pathological activity often observed in epilepsy [Time Frame: Up to 6 weeks]

The effect of the sensory flicker will be evaluated by the comparison of the whole-brain rate of IEDs between sensory flicker stimulation and baseline (no stimulation).

1.3.3 Exploratory Outcome Measures:

- 1) To study whether sensory flicker exposure can entrain LFPs and modulate single neuron activity in higher cognitive areas such as the hippocampus and prefrontal cortex.
- 2) To identify the modality and frequency of flicker to which given brain regions are most efficiently modulated at the LFP and the single unit levels.
- 3) To identify potential effects of audiovisual flicker on various cognitive processes through a behavioral task.
 - a. If there are effects, to identify their electrophysiological correlates (such as changes in sharp-wave ripples' rate).
- 4) To compare the effects of sensory flicker modulation to direct electrical modulation of various neural circuits within individual subjects.

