2.2.11. Source records and data collection

Data will be collected from either the subjects' electronic medical records (EMR), the EMU medical Natus neurophysiological recording system, or via devices and custom softwares mentioned above (2.1). Data collected in the subjects' EMRs will include metadata pertinent to this study, including age, determination of the seizure onset zone location and seizure medications taken on the day of the experiment.

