5. STATISTICAL ANALYSIS

For objectives 1 and 2, we will perform analyses similar to the ones used in Martorell et al.'s study². We will perform a power spectral density analysis of LFP signal in function of frequency and modality (visual, auditory or audiovisual) of the sensory flicker stimulus, using multi-taper methods. Comparisons will be drawn between the mean power spectral density under a given condition and control (random sensory flicker or no flicker) condition, using the Wilcoxon rank-sum test with Bonferroni correction for multiple comparisons. To analyze firing rate modulation of single units to sensory flicker, we will produce a histogram of each single unit's firing rate

aligned to the onset of light and/or sound stimulus. Moreover, we will analyze how strongly the firing rate of single units is phase-locked to the stimulus being played, by calculating and comparing the vector strength of their firing rate modulation under different conditions, using the Kolmogorov-Smirnov test.

For objective 3, we will use similar methods as mentioned above, and compare the effect size of LFP entrainment and firing rate modulation in different brain regions, in function of various sensory flicker parameters (i.e. frequency and modality).

For objective 4, we will do within-subject comparison of the rate of interictal epileptiform discharges during various stimulation and/or baseline conditions. If normally distributed we will use t-test to compare the conditions, otherwise we will use repeated-measures ANOVA.

For objective 5, memory performance will be compared with a repeated-measures ANOVA across the different conditions (e.g. for example, 5.5Hz or 40Hz audiovisual flicker vs. random audiovisual flicker). For one of the memory experiments, performance in the case of random flicker will serve as the baseline from which we will infer any improvement or impairment in memory performance.

All neural data analyses will be performed in Python and/or MATLAB.

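### The repeated consolidation experiment (2.2.8) sets no order of conditions and no session term, although its memory test can be unexpected at most once; this should be fixed in the design and the model

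*Combined protocol and SAP*

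**What the plan says.** Section 2.2.8 describes a study phase, 36 minutes of audiovisual flicker (random, 5.5 Hz or 40 Hz), and then a surprise test of item and source recognition: "Finally, they will undergo an unexpected test of memory for the words or images". Repetition is optional: "depending on his or her choice, a patient may go through the task more than once on different days", with a different flicker condition each time. The purpose is stated: "This would allow us to compare the effects of specific frequencies of audiovisual flicker on memory, in the same patients". The paradigm itself is left loose: "subjects may go through the following experimental paradigm or a similar one".

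Section 5 (objective 5) gives the analysis: "memory performance will be compared with a repeated-measures ANOVA across the different conditions". One memory experiment also has a named reference condition: "performance in the case of random flicker will serve as the baseline from which we will infer any improvement or impairment". Section 2.2.8 is the memory experiment that lists a random-flicker condition.

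Neither section says how the order of conditions is chosen, whether items differ between days, or how a patient with only one or two conditions enters the analysis. No session, day or order factor is named. The word random in these sections describes a type of flicker, not an allocation.

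The outcome is exploratory (section 1.3.3, third item): "To identify potential effects of audiovisual flicker on various cognitive processes through a behavioral task".

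**The concern.** After the first session a patient knows that a test follows the flicker and has practised it. The plan describes nothing that would keep later tests a surprise. Later sessions therefore differ from the first in a way unrelated to flicker, and the within-patient comparison is built on them.

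The direction is open. Expectation and practice could raise later scores. Fatigue or clinical change during the 2-4 week stay (section 4.4) could lower them. Section 2.2.11 collects "seizure medications taken on the day of the experiment", so the patient's state may differ between days.

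Two things are at stake. If the order is clearly lopsided, a session effect could be reported as a memory gain or loss from flicker. If the order is balanced, that bias disappears, but session variation stays in the error term and costs power. In addition, a standard three-condition repeated-measures ANOVA uses only patients with all three conditions, while the number of sessions is the patient's choice.

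**Working it through.** The documents give no sample size, SD, effect size or session effect for this experiment, so there is no planned figure to reproduce. The figures below are illustrations on assumed inputs: 20 patients with two sessions each, within-session SD 10 points, a shift *d* in the second session, two-sided alpha 0.05.

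**Bias.** Let *p* be the share of patients with random flicker first. The flicker-minus-random difference picks up +*d* when random comes first and −*d* when it comes second, so bias = (2*p* − 1) × *d*. With *d* = 5: 0 at *p* = 50%, 0.6 × 5 = 3 points at 80%, and 5 points at 100%.

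**Type I error.** With two conditions the planned ANOVA is a paired t test. The SE of the mean difference is 10 × √2 / √20 = 3.16 points. Simulation with no true flicker effect gives:

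| Share with random first | *d* = 2 | *d* = 3 | *d* = 5 | *d* = 10 |
|---|---|---|---|---|
| Coin flip per patient | 5% | 5% | 5% | 5% |
| 50% (exact balance) | 5% | 5% | 4% | 2% |
| 60% | 5% | 5% | 5% | 4% |
| 70% | 6% | 6% | 8% | 13% |
| 80% | 6% | 8% | 13% | 32% |
| 100% | 9% | 15% | 32% | 85% |

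A fall in later scores gives the same rates with the sign of the bias reversed. With a session term, type I error is 5% whenever both orders occur. At 100% random-first, condition and session coincide and the contrast cannot be estimated.

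**Power under balanced order.** Without a session term, the shift enters the residual. At *d* = 5 the estimated SE is about √[(200 + 25 × 20/19)/20] = 3.36 instead of 3.16; at *d* = 10 it is √[(200 + 100 × 20/19)/20] = 3.91. For an assumed true effect of 8 points:

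| | *d* = 3 | *d* = 5 | *d* = 10 |
|---|---|---|---|
| Planned ANOVA | 65% | 62% | 49% |
| With session term | 67% | 67% | 67% |

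**Incomplete patients.** Assume 36 patients, 12 each with one, two and three sessions, all six orders, and between-patient SD 10 or 15. The SE of a pairwise contrast is:

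- three-session patients only: 10 × √(2/12) = 4.08;
- paired analysis that also uses the 4 two-session patients for that pair: 10 × √(2/16) = 3.54;
- mixed model with session number, patients with two or three sessions: 3.27 to 3.30;
- the same model, all patients: 3.11 to 3.19.

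Most of the gain comes from keeping the two-session patients.

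**The case against.** The strongest reply is that this concerns silence, not an error. The plan nowhere says the order will be lopsided. At 60% random-first there is no inflation, and at 70-80% a shift of 2-3 points gives only 6-8%. The large figures need a strong imbalance together with a shift of 0.5 to 1 within-session SD, and the documents give neither. The outcome is exploratory, repeats are optional, and if each patient did one session the order problem would not arise. A single sentence promising randomised or counterbalanced order would remove the bias.

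Most of this stands and limits the weight of the point. It does not remove it. Order has to be fixed before sessions are run, because nothing later can rescue a comparison in which random flicker always came first. Balancing alone also does not recover the lost power or say what happens to incomplete patients.

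Three stronger readings are tempting and are not supported:

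- A reader might infer that random flicker, as the stated baseline, will be run first. The plan does not say so.
- A reader might infer that the first test is certainly a surprise. It may not be: the recruiter explains the procedures at consent (section 4.3; the form is not available here), and a patient may already have taken the 2.2.7 memory test. Hence at most once.
- A reader might infer that all memory results are exposed. In 2.2.7 flicker is paired with some items within a session, so the concern does not carry over.

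**Conclusion.** The point holds as a design and analysis improvement for one exploratory experiment. The conflict between a surprise test and its repeated use is in the text, and so is the absence of an order rule and a session term. Bias is conditional: none on average with balanced or coin-flip order; with a 5-point shift and 20 patients, type I error of 13% if 80% have random flicker first and 32% if all do. Even under balance, the planned ANOVA gives 62% power against 67% with a session term at that shift. The gap is trivial at 3 points (65% against 67%) and large at 10 (49% against 67%). All of these figures rest on assumed SD, shift, effect and sample size. The primary LFP and secondary IED outcomes are unaffected.

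**What to change.** For 2.2.8 only:

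1. Assign the order of conditions per patient from a randomised list balanced over all six orders. Balance then also holds for patients who stop after one or two sessions. A single cyclic Latin square would not do this: among two-session patients it puts random flicker first in every random-versus-5.5 Hz pair, or last in every one. Use a different item list in each session, with lists balanced over conditions.
2. In Section 5, analyse this experiment with a linear mixed model: condition and session number as fixed effects, a patient random intercept, and every patient with at least one session included. Under balanced order this is for power and for keeping incomplete patients; it is not needed for type I error. The ANOVA can stay for the other memory experiments.
3. Describe the test as unexpected in the first session at most.

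No separate first-session analysis is needed. With 12 patients per condition and between-patient SD 10 to 15, its 95% interval would be about ±12 to ±15 points (2.035 × 5.77 to 2.035 × 7.36), too wide to inform.

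The cost is a randomisation list, two further item lists and SAP wording, with no extra sessions. Session number uses one degree of freedom with two sessions and two with three. The model assumes that flicker acts similarly on expected and unexpected tests, which should be stated.

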2.2.9. COVID-19 related procedure

Our study subjects are inpatients undergoing intracranial seizure monitoring as part of an evaluation for epilepsy surgery. As part of their clinical care, they are continuously video-monitored for seizure semiology, including facial movements that could be critical to understanding their seizure network; furthermore, sometimes they only have very few seizures

while admitted and getting maximal information from each seizure is critical in determining the surgical approach. Thus, having them wear a mask during a research study session, or during the consent procedure if performed while they are already inpatients, would constitute a substantial departure from their clinical care. As such, we ask for an exemption for our study subjects to wear a mask during interactions with researchers, while they are inpatients and being video-monitored for seizure semiology. Researchers will still wear a mask during any interaction with the patient.

Note: all of our participants are tested for SARS-CoV-2 virus before admission.

2.2.10. Research data storage

Data containing protected health information (PHI), such as link between subjectID and patient name, date of birth and other PHI, will be saved on a secure platform, such as Emory OneDrive.

Data that has been deidentified may be stored indefinitely on various platforms, such as Emory REDCap and the lab server. For example, de-identified metadata, such as patient neuropsychological testing results, MRI reports, electrode implant details, and experiment notes, may be stored on REDCap; other de-identified data, such as imaging, neurophysiological recordings and analysis data, may be stored on the lab server.

2.2.11. Source records and data collection

Data will be collected from either the subjects' electronic medical records (EMR), the EMU medical Natus neurophysiological recording system, or via devices and custom softwares mentioned above (2.1). Data collected in the subjects' EMRs will include metadata pertinent to this study, including age, determination of the seizure onset zone location and seizure medications taken on the day of the experiment.

2.2.12. Long term follow up

Once all research-related procedures are complete, missing data pertinent to the research study may be collected, either in the subjects' EMRs or on the EMU Natus clinical EEG server.

3. RISK ASSESSMENT

There are no direct benefits to participants in this study. However, this study will provide a better understanding of how sensory flicker affects activity in various brain areas relative to direct electrical stimulation, and whether it can impact memory performance or interictal epileptiform discharges. The gains from this study are anticipated to help develop new non-invasive treatments for several brain diseases such as epilepsy, Alzheimer's Disease, depression and obsessive-compulsive disorder.

All subjects will have already undergone an operation to implant macroelectrodes as is necessary for clinical evaluation and treatment. Additional microelectrode contacts are built into the clinically necessary macroelectrodes and are placed in the same surgery. Thus, the current proposal does not present additional risk from additional surgeries.

Every precaution is taken to minimize risks.

3.1. Electrical brain stimulation

Direct electrical brain stimulation is a routine procedure in the Epilepsy Monitoring Unit for localization of brain function and confirming regions of seizure onset in patients with intracranial electrodes. Safety limits have been established for decades^{37,38}. Stimulus trains will utilize current regulated, charge-balanced, biphasic rectangular pulses set below the afterdischarge threshold. Stimulation trains will be brief (less than or equal to 10 seconds) and stimulation levels will be kept below the safety limits identified by histological analysis for chronic ($30 \mu\text{C}/\text{cm}^2$ per ph) and acute ($57 \mu\text{C}/\text{cm}^2$ per ph) stimulation protocols^{37,38}.

Brain stimulation can, particularly when applied to a seizure onset zone, cause afterdischarges (brief, localized, epileptiform activity), which are often asymptomatic. Afterdischarges are generally self-limiting but can elicit an actual seizure if repeated or prolonged. Brain stimulation can also elicit clinical seizures, which usually resemble the subject's habitual seizures. The risk of seizure is small and well known to clinicians performing stimulation for functional localization. Moreover, in a recent research study using electrical brain stimulation in patients (770 stimulation sessions across 188 patients), seizure occurred during or within 30 minutes of the stimulation session for less than 2% of sessions (Goldstein et al., In Prep). We have proposed to use stimulation parameters that are less likely to induce afterdischarges, and therefore less likely to induce seizures^{29,31,33,34}.

We will take the following steps to prevent risk of inducing a seizure:

- Under the supervision of a qualified medical personnel (neurologist, neurosurgeon, or neurology fellow familiar with brain stimulation for epilepsy) we will test different stimulation amplitudes to determine a threshold at which afterdischarges are observed. Subsequent stimulation currents used during stimulation sessions will be kept 25-30% below the afterdischarge threshold to mitigate risk of seizure, and these stimulation current levels will have to be approved by qualified medical personnel.
- During all stimulation sessions, the subject's clinical EEG will be monitored in real-time for afterdischarges by qualified medical personnel or intracranial monitoring reader. If any afterdischarges are observed, the protocol will be immediately halted and the patient assessed. Once afterdischarges have stopped, stimulation current will be decreased by a further 25-30% and testing will resume. If afterdischarges occur again, the protocol will be halted and stimulation sessions will be cancelled for the patient.
- No stimulation will be attempted within 2 hours of a spontaneous seizure.

If at any time clinical seizures are elicited during stimulation, the protocol will be halted and stimulation sessions will be cancelled for that patient. Seizure monitoring units have protocols in place to treat seizures. Clinical seizures that occur during the time of the stimulation sessions will be reported to the medical monitor. The patient will be informed about the risk of seizure as done in routine clinical functional mapping.

Brain stimulation may also temporarily induce unusual sensations such as tingling, movement, interruption of speech and change in mood. If this occurs and makes the patient uncomfortable, we will decrease the stimulation amplitude by 25-30% and reassess.

